The theory of change (ToC) is a key output of the discussions with PACT and Foundations during the evaluation set-up stage and ToC workshop. The ToC sets out the mandatory inputs and activities (i.e. **Referral and triage process; groups sessions; staff training; and offboarding**) for successful delivery. The key inputs and activities are discussed in more detail in the sections below. The referral and triage process is essential to ensure parents and children have access to the appropriate support. The training enables staff to successfully provide support and deliver the weekly sessions. The group element of the sessions is considered an important mechanism as it provides adults and children with a supportive group environment where they can experience connection with other families with similar experiences. This helps to reduce loneliness for both the parent and child, and in turn can increase the parent's agency and self-efficacy. As can be seen in the stated ToC, BB4K aims to improve the child's and the parent's abilities to identify healthy and unhealthy behaviours, to emotionally regulate, and to have a clearer understanding of each other's responsibilities in the short term. As a result, it is anticipated that parents and children can avoid unhealthy behaviours and will seek support when needed. The ToC considers those improvements as essential elements for the medium-term outcomes (i.e. parent better able to understand and advocate for child's needs; healthier parent-child relationship; improved parent/child communication; increased parent DA reporting; and reduced child behavioural issues) and long-term outcomes (i.e. reduced parental stress; reduced repeat victimisation; repaired attachment patterns between parent and child; and improved family functioning) to be realised.

It is important to note that the evaluation is designed to assess impact in a robust way for three outcomes (highlighted in green in the ToC linked above). The outcomes were selected jointly with PACT based on their centrality to the ToC. When deciding, the evaluator also considered the practical and financial limitations placed on this study.

Referral and triage

BB4K accepts referrals into the service from local authorities (primarily children's services, adult social care, and housing), schools, community partners, counselling services and other charities. BB4K also accepts self-referrals from parents.

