- Non-perpetrating parent and child not currently receiving other domestic abuse support
- Children and non-perpetrating parent live in Reading, West Berkshire, or Vale of the White Horse in Oxfordshire
- The perpetrator parent must have left the family home and be out of the relationship for at least a month⁹
- The referral falls within the trial period as defined above
- Referred parents provide consent: they agree that they and their child can participate in the evaluation: are willing to be randomly assigned to treatment or waitlist treatment group, complete questionnaires at three time points and potentially take part in qualitative discussions.

Sample size/MDES calculations

		MDES (Proportion of a Standard Deviation)
MDES		0.79
Baseline/Endline correlations	Child	N/A
	Participant (parent/child)	0.56
	Social Worker	N/A

⁹ If the parent had split from the perpetrator less than a month ago, PACT will need to consider if safe engagement can be enabled. PACT also monitors during delivery if parents reengage with perpetrators: first, at the point of referral and triage, and this is captured in their CMS, Lamplight, and second, support workers document in their post-session notes.

Intracluster correlations (ICCs)	Family	N/A
	Site	0
	Group	0.1
Alpha		0.05
Power		0.8
One-sided or two-sided?		Two-sided
Level of intervention clustering		Treatment groups
Average cluster size		9
Sample size (parent–child pairs)	Intervention	40
	Control	32
	Total	72

The power calculations assume 5:4 allocation to treatment and waitlist treatment groups. In total, 9 groups will participate in the trial, out of which five will be assigned to the treatment, and four will be allocated to the waitlist treatment. This will result in a total of nine clusters of eight parent–child pairs. It was assumed that 72 eligible parent–child pairs would be randomised, with 40 in the treatment, and 32 in the waitlist treatment groups. We further assumed the within-participant correlation to be 0.56 based on a similar study.¹⁰ We assumed that the outcomes would not be related to the delivery site. The intervention is delivered in groups, therefore there is a potential for clustering in the treatment arm (with no such effect in the waitlist treatment). The degree of this

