Given that PACT collects TOPSE (parental self-efficacy) as part of usual practice, they will collect the questionnaire from participating parents and will share the data with IFF, while IFF research will collect data on the secondary outcome measures (i.e. BAC-C and CPRS) from participating parents through parent-administered surveys. This approach has been taken to keep data collection from participants as minimal as possible in line with ethical good practice.

Parents will be given the questionnaire to fill in on their own without PACT present.

The researchers scoring the data will not be blind to intervention allocation. If the parent reveals their allocated treatment group to the researcher, this will be recorded.

The baseline and follow-up surveys will be sent via email and IFF will follow-up with reminder emails and telephone calls. Parents in the treatment group will complete the endline survey in the final session. PACT will extend the last session by 15 minutes to give parents time to complete the survey. Parents will be encouraged to complete the survey on their own device (e.g. their phone), but PACT will provide an alternative if needed (e.g. using a PACT laptop). Parents and children in one of the Cohort 1 waitlist treatment groups will complete the endline survey during an in-person event (for more information on the event please see the [Experiment 1: Testing use of in-person events](#)). For groups not involved in-person experiment events, parents will be sent the surveys via email by IFF to complete.

The study acknowledges that the different approaches to outcome measure deployment between the treatment group and the waitlist treatment group has the potential to introduce different biases. Though PACT may not be present, the treatment group's TOPSE being organised by PACT for the baseline and endline still may influence responses, for example by increasing the likelihood of socially desirable answers. Conversely, the waitlist treatment group receiving all measures via email may increase the potential of experiencing technical issues filling in the survey or not being able to ask for clarity on questions as they will not be in regular contact with PACT.

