The primary outcome is the TOPSE score at follow-up,¹⁸ controlling for baseline TOPSE score. We will estimate the mean difference in TOPSE scores between participating families in BB4K and the waitlist treatment group participants. The primary analysis will use a mixed effects model allowing for different outcome variance between the treatment group and waitlist treatment group arms, and heteroscedastic individual-level errors. The model will control for delivery site, child age,¹⁹ and baseline TOPSE score via fixed effects. The between-cluster variation in the treatment group groups will be modelled as a random effect. The model is not powered to investigate differences in treatment effects between sites.

The analysis model will be:

$$Y_{ijk} = \beta_0 + \sum_{k=1}^3 \beta_k s_k + \gamma Y_{0ijk} + \delta X_{ijk} + \theta t_{ijk} + t_{ijk} u_{jk} + (1 - t_{ijk}) r_{ijk} + t_{ijk} \varepsilon_{ijk}$$

- Y_{ijk} is the outcome at follow up for parent i in treatment group j and sites k
- There are three sites $k= 1,2,3$
- There are $j=9$ clusters corresponding to 5 treatment group and 4 waitlist treatment groups
- Sites $k=1,2,3$
- β_k represents difference in outcomes between sites
- θ is the treatment effect.

In line with Foundation's Statistical Guidance, the analyses will follow an intention-to-treat (ITT) approach. The analysis will include all randomised children and parents in the groups to which they were randomly assigned, regardless of the treatment actually received, withdrawal from BB4K post-randomisation, or deviations in programme implementation. This principle is key in ensuring an unbiased analysis of intervention effects. The difference between the treatment and waitlist treatment groups at endline will be expressed as a standardised effect size using Hedges' g with 95% confidence intervals. The primary analysis will also include detailed descriptive analysis: histograms, means, quartiles, and standard deviations, for all measures, groups, and time points. All analysis will be scripted to allow for transparency and replication and will be uploaded to GitHub.

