Upon receipt from PACT, a researcher will conduct an initial check of the data received against our IPE MI plan and follow up with PACT to fill data gaps and clarify any discrepancies. After we are confident we have the correct data, our data services team processes the data (e.g. ensures consistent formatting; reorganises it for evaluation purpose) and creates an SPSS file and tables for descriptive analysis using a data specification the research team develops. The process is repeated at Wave 2 (the final analysis wave) and tables are created that show change between waves 1 and 2.

Triangulation

We will take a systematic approach to the analysis of all strands of data collection (impact and IPE) to generate insight that covers both the breadth of all participating families and the depth of experiences and impacts for different types of families (different Cohorts or younger/older age groups). To incorporate the information from all strands of data collection we will design an analysis framework. The framework will be structured around the research questions. It will be set up to allow us to identify differences across parents and children and stakeholder groups. We will organise an internal analysis workshop to triangulate the evidence gathered into a coherent set of findings; to explore possible convergence and divergence of trends and themes and anticipate their plausible outcomes; and draft recommendations for the programme.

Evaluation experiments

We will conduct two experiments to answer RQ4 of the implementation and process evaluation, focusing on strategies to boost response rates to the endline and follow-up surveys. The experiments will be conducted 5 months after randomisation. At this point, waitlist treatment groups have not yet taken part in BB4K. These experiments include:

1. Testing use of in-person events for survey completion
2. Testing use of £10 incentives on endline survey response.

Experiment 1: Testing use of in-person events for survey completion

Experiment 1 involves testing the use of in-person events on follow-up survey completion with Cohort 1 only. Cohort 1 has two treatment groups and two waitlist treatment groups (32 families total). One treatment group and one waitlist treatment group will take part in the celebration events (16 families) and the other treatment and waitlist treatment groups will not (16 families).

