Treatment group celebration event: PACT will host an in-person event with one of the Cohort 1 treatment groups (selected by IFF using a random number generator) during the follow-up survey collection period at the end of September 2024. All parents and children who took part in the group will be invited via email to attend the ‘coffee morning’ celebration event and come back together a few months after their last session to reconnect and reflect on their successes.

Waitlist treatment group introduction event: PACT will host an in-person event with one of the Cohort 1 waitlist treatment groups during the endline survey collection period at the end of September 2024. IFF will randomly select the groups using a random number generator. All parents and children from one of the waitlist treatment groups, will be invited via email to attend the ‘coffee morning’ introductory event and come together to meet for the first time and learn more about what BB4K will entail.

PACT will host both events at the same location where the groups sessions are held. Events will be hosted during school hours to ensure accessibility, familiarity, and available childcare. Children will not be required to attend but parents may wish to bring along those under school age. PACT will provide tea, coffee, and cakes to encourage families to attend.

IFF will issue the follow-up survey to both groups a week before the event. During the events two researchers from IFF Research will speak to the groups about the importance of their involvement in the evaluation. They will bring laptops and offer to help parents complete the survey in-person during the event. Parents who do not attend the event and do not complete the survey following the email invite and two reminders, will receive a phone call from an IFF telephone interviewer, asking the parent to complete the survey over the phone.

For groups in Cohort 2 – not involved in this experiment – surveys will be administered by email at the time indicated in the project timetable.

Reporting results: The interim and final reports will discuss the results of Experiment 1, specifically, the effectiveness of the celebration groups by comparing response rates in the treatment group participating in the experiment to response rates in the treatment group not participating in the experiment, and similarly for the waitlist treatment groups.

Experiment 2: Testing use of incentives

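### Experiment 1 invites parents to complete the follow-up survey during PACT-hosted events whose content could itself shift the primary outcome; the survey should come before that content

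*Protocol*

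**What the plan says.** Under Primary analysis the protocol states: "The primary outcome is the TOPSE score at follow-up". The Data collection timetable puts Cohort 1 follow-up in September to October 2024.

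Experiment 1 tests whether in-person events improve completion of the follow-up survey in Cohort 1. One treatment group and one waitlist group are picked at random. PACT hosts both events at the session venue at the end of September 2024.

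- Treatment families are invited to "come back together a few months after their last session to reconnect and reflect on their successes".
- Waitlist families are invited to "come together to meet for the first time and learn more about what BB4K will entail".
- The evaluator issues the follow-up survey to both groups a week earlier and sends two researchers to each event: "They will bring laptops and offer to help parents complete the survey in-person during the event".

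Three other passages bear on this.

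- Data collection sets a general rule: "Parents will be given the questionnaire to fill in on their own without PACT present". It also discusses bias from deploying the measures differently in the two arms. It does not treat the events as extra programme contact.
- The Theory of change section says of the supportive group setting: "This helps to reduce loneliness for both the parent and child". It adds that this can in turn raise the parent's self-efficacy.
- The documents disagree about the waitlist event. Data collection, and one sentence of Experiment 1, attach it to the endline survey. The rest of Experiment 1 attaches it to follow-up.

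**The concern.** TOPSE is a self-reported self-efficacy scale. A gathering where treated parents look back on what they achieved, or where waitlist parents first meet their future group, is the kind of contact that the protocol's own theory says can raise self-efficacy. A parent who answers during or after it is not measured under the same conditions as the families with no event.

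The contrast of interest is the group sessions against Bounce plus usual support. Extra contact before or at the primary measurement adds something else to that contrast, and adds something different in each arm. The analysis model has no event term. With one event group per arm, an event effect cannot be told apart from that group's own level. The contamination is therefore easier to prevent in the event agenda than to remove in the analysis.

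**Working it through.** **1. Families involved.** The sample size section says "This will result in a total of nine clusters of eight" pairs. Two event groups give 2 x 8 = 16, which matches the plan's own count in Experiment 1 ("One treatment group and one waitlist treatment group will take part in the celebration events (16 families", in its words). As shares:

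- all randomised: 16/72 = 22.2%
- treatment arm: 8/40 = 0.20
- waitlist arm: 8/32 = 0.25

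**2. Timing.** Cohort 1 endline is July to August 2024 and follow-up is September to October 2024. An event at the end of September falls in the follow-up window and outside the endline window.

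**3. Is TOPSE in the event survey?** Data collection first says PACT collects TOPSE and the evaluator collects the two secondary measures. It later names PACT-organised TOPSE in the treatment arm only at baseline and endline, and says follow-up surveys go out by email with evaluator reminders and calls. Inclusion of TOPSE is the better reading but is not stated. If TOPSE is collected separately, the events still fall within its window.

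**4. Size.** Let dT and dW be the shifts in TOPSE, in SD, that an event produces in treatment and waitlist families. If every event family is affected, the mean difference moves by

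shift = 0.20 x dT - 0.25 x dW.

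The protocol gives no event effect, so every dT and dW below is an assumption.

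| dT | dW | Shift (SD) | Size relative to 0.79 |
|---|---|---|---|
| +0.25 | 0 | +0.05 | 6% |
| +0.5 | 0 | +0.10 | 13% |
| +1.0 | 0 | +0.20 | 25% |
| 0 | +0.5 | -0.125 | 16% |
| +0.5 | +0.5 | 0.10 - 0.125 = -0.025 | 3% |
| +0.5 | -0.5 | 0.10 + 0.125 = +0.225 | 28% |

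**5. Scaling down.** Only families exposed to event content before they answer count. If half of each event group is in that position, each figure halves; the one-arm 0.5 SD cases become +0.05 and -0.0625 SD.

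**6. If the waitlist event collects only endline.** Primary data taken at an event then cover at most 8 of 72 families (11.1%). The waitlist group would still have met and heard about the programme by the time of its follow-up, so dW need not be zero.

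**7. Cost of dropping both event groups in a sensitivity analysis.** This leaves 40 - 8 = 32 and 32 - 8 = 24 families. Ignoring clustering, the standard error grows by sqrt(1/32 + 1/24) / sqrt(1/40 + 1/32) = 0.270/0.237 = 1.14, about 14%.

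**The case against.** The strongest reply has five parts.

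- **TOPSE at the event is inferred.** A reader might conclude that the primary TOPSE is definitely collected there from up to 16 families. The documents do not go that far: TOPSE is also assigned to PACT, and the waitlist event is twice labelled endline. This stands, and the point is conditional for that reason.
- **A safeguard exists.** The survey goes out a week before, so parents who answer promptly are measured before any event content, and attendance is voluntary. This stands, and makes 8 and 8 a ceiling.
- **PACT's presence is not stated.** A reader might infer that parents complete the scale in front of the provider, in breach of the rule in Data collection. Hosting an event is not the same as being in the room, the help comes from the evaluator, and nothing in Experiment 1 withdraws the rule. What remains is that Experiment 1 does not say how the rule will be kept.
- **The effect may be trivial.** A 0.5 SD shift from one coffee morning is 63% (0.5/0.79) of the MDES for the whole programme and has no support in the protocol. Both events bring parents together, so their effects could largely offset. This stands as to size. Because the content differs, offsetting cannot be assumed.
- **This is a pilot in which low response is a named risk.** Testing a retention method inside it is a deliberate and reasonable trade-off. Agreed, and the fix leaves that test in place.

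The event groups are also chosen at random, so this is contamination of the measurement and not selection into events.

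**Conclusion.** The concern holds as an avoidable source of bias of modest size and unknown direction. Experiment 1 fixes the host, venue, timing and content of the events and offers survey completion during them, without saying that measurement comes before the content.

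At the ceiling the primary estimate moves by 0.20 x dT - 0.25 x dW. Under the illustrative 0.5 SD assumption that is +0.10 or -0.125 SD if one arm moves, -0.025 SD if both move equally, and +0.225 SD if they move in opposite directions. All are well below 0.79. The conclusion rests on three things: events held in late September, as dated; some attenders not having responded beforehand; and event contact being able to affect self-efficacy, which the theory of change supports in direction but not in size.

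The documents do not support saying that the primary result will be materially biased, or that the two events' effects cannot cancel. The conflict over which survey the waitlist event collects is a plain inconsistency and needs correcting in any case.

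**What to change.** 1. State in Experiment 1 that attenders who have not yet responded complete the survey on arrival, alone and with PACT out of the room, before any reunion or introduction content. Limit evaluator help to technical problems.
2. Record for each survey how it was completed (email, event or telephone) and when.
3. Add a sensitivity analysis of the primary outcome that drops the two randomly chosen event groups whole. Do not exclude individual surveys by when they were completed, because that selects on behaviour after randomisation. The two dropped groups may differ in age band or site, so keep the planned adjustment for both.
4. Reconcile Data collection with Experiment 1 on whether the waitlist event collects endline or follow-up, and state whether the follow-up survey includes TOPSE.

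The cost is a slightly less relaxed start to each event, one extra data field, and a sensitivity analysis with a standard error about 14% larger. The response-rate comparison is kept.

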Experiment 2 tests the use of incentives on endline survey completion with Cohort 2 only, in January 2025. Cohort 2 has three treatment groups and two waitlist treatment groups (40 families total). We will explore the effect of offering £10 incentives for endline survey completion with two treatment and two waitlist treatment groups in Cohort 2 (32 families). IFF will randomly select the groups using a random number generator.

Those groups selected will be notified of the opportunity to receive the incentive when they're invited via email to complete the survey. At the end of the survey, they will be able to select from a £10 Amazon voucher or a £10 Love2Shop voucher and asked to provide an email address to receive the voucher. Those selected for the incentive who do not respond to the email prompts will be notified of the incentive when they receive a phone call asking them to complete the survey.

Reporting results: The final report will discuss the results of Experiment 2, specifically, the effectiveness of the incentives by comparing response rates in the treatment group participating in the experiment to response rates in the treatment group not participating in the experiment, and similarly for the waitlist treatment groups.

Cost evaluation

The overall aim of the cost evaluation is to understand the additional costs and, where possible, benefits of the programme compared to if it was not delivered. Our proposed approach is to calculate **the overall cost for BB4K delivery, and the unit cost per family and per each of the three sites.**

Costs will be based on the resources needed to roll out BB4K in comparison to 'business as usual'. In line with the WWCS cost analysis guidance, we will split costs into prerequisites (e.g. access to facilities to deliver, overheads), start-up (e.g. the purchase of equipment, training staff cost, salaries) and recurring delivery costs (e.g. non-durable materials, costs for new staff).

Outside the cost evaluation we will present separately costs of parents' time, children's time, and volunteers' time

As a first step we will calculate the overall costs at BB4K level. We will ask PACT to provide information on the following cost categories:

- Staff costs: including salaries, National Insurance Contributions, pensions for all workers including temporary and contract workers; if staff don't spend all of their time on BB4K, we will ask PACT to confirm the time allocated for the year to BB4K
- Volunteer time, if any

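### Experiment 2 offers the £10 incentive to both of Cohort 2's two waitlist groups, so the planned waitlist response-rate comparison has no comparator

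*Protocol*

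**What the plan says.** All of the relevant text is in the Protocol, under 'Evaluation experiments', 'Experiment 2: Testing use of incentives'.

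- Scope: "Experiment 2 tests the use of incentives on endline survey completion with Cohort 2 only, in January 2025".
- Groups available: "Cohort 2 has three treatment groups and two waitlist treatment groups (40 families total").
- Groups offered the voucher: "for endline survey completion with two treatment and two waitlist treatment groups in Cohort 2 (32 families").
- How they are chosen: "IFF will randomly select the groups using a random number generator".
- What being chosen means: "Those groups selected will be notified of the opportunity to receive the incentive when they're invited via email to complete the survey".
- What will be reported: response in the participating treatment group is set against response in the "treatment group not participating in the experiment, and similarly for the waitlist treatment groups".

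The summary table under 'Randomisation' and the survey schedule under 'Data collection' also give Cohort 2 two waitlist groups. The first of these shows one group aged 3–5 and one aged 6–11.

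**The concern.** A with-and-without comparison needs some families without. The plan names as many incentivised waitlist groups as Cohort 2 contains, so nobody in that arm is left to compare with. One of the two results promised for the final report then cannot be produced at all, however well the survey runs, and it cannot be recovered once every waitlist family has had the offer.

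The missing half is also the more useful one. Under 'Data collection' and 'Early impact analysis using the endline survey', treatment parents complete the endline questionnaire in an extended final session, whereas the waitlist arm is generally emailed it. Email is also how the voucher is announced. Waitlist retention and low survey response are both rated medium/high in the risk table. Experiment 2 is the only test of incentives in the Protocol.

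**Working it through.** **Inputs**
- Cohort 2 groups: 3 treatment, 2 waitlist ('Experiment 2'; the same in the 'Randomisation' and 'Data collection' tables).
- Incentivised groups: 2 treatment, 2 waitlist ('Experiment 2').
- Families per group: 8, from 'Sample size/MDES calculations': "This will result in a total of nine clusters of eight parent–child pairs".
- These are planned maxima; the 'Randomisation' table gives Cohort 2 as up to 40 pairs.

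**Step 1: reproduce the plan's own figures**
- Cohort 2 total: (3 + 2) × 8 = 40. Matches.
- Incentivised: (2 + 2) × 8 = 32. Matches.

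The 32 families agree with two waitlist groups, so that count is not an isolated slip.

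**Step 2: who is left without the offer**

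| Arm | Offered | Not offered | Ways to select the groups |
|---|---|---|---|
| Treatment | 2 × 8 = 16 | (3 − 2) × 8 = 8 | C(3,2) = 3 |
| Waitlist | 2 × 8 = 16 | (2 − 2) × 8 = 0 | C(2,2) = 1 |

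The treatment contrast is two groups v one, 16 v 8 families. The waitlist contrast is 16 v 0. With only one way to choose two groups from two, the random number generator decides nothing in that arm.

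**Step 3: can 32 families be kept?**

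With whole groups of eight, 32 families means four groups. The only splits are 2 treatment + 2 waitlist, which leaves no waitlist comparator, and 3 treatment + 1 waitlist, which leaves no treatment comparator. If whole groups are offered the voucher, 32 families and a comparator in both arms cannot both hold.

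**Step 4: what a repaired waitlist contrast would give**

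Offering the voucher to half the families in each waitlist group gives 4 + 4 = 8 offered and 8 not. The total offered becomes 16 + 8 = 24.

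Assume response of 80% with the voucher and 60% without; neither figure is in the Protocol. The 95% half-width for the difference is

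1.96 × √(0.8 × 0.2/8 + 0.6 × 0.4/8) = 1.96 × √(0.02 + 0.03) = 1.96 × 0.2236 = 0.44,

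or about 44 percentage points. The contrast would exist, but could only be described.

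**The case against.** The best defence is that the four groups are the pool for the experiment and that the voucher groups are then drawn from within it. This would echo Experiment 1, which also involves four groups and 32 families with half exposed. The references to selected groups, and to families selected for the incentive, lend it some support. It fails on two counts. The comparator is defined as groups "not participating in the experiment, and similarly for the waitlist treatment groups", and no Cohort 2 waitlist group lies outside the four. Also, no split within the four is stated, whereas Experiment 1 states which groups do and do not get the event. If the pool reading was intended, the text still has to be rewritten to say so.

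Nor can the Cohort 1 waitlist groups serve as comparator. The experiment is confined to Cohort 2, and Cohort 1's endline was scheduled for July–August 2024, so that comparison would be neither randomised nor concurrent.

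It is also fair to object that little is lost. Experiment 2 concerns response to the endline survey, the primary outcome is measured at follow-up, and even a repaired 8 v 8 comparison is very imprecise. That stands, and it limits the severity. It does not rescue a reported comparison that has no second arm.

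A reader might go further and infer that the unequal offer in Cohort 2 (16/16 waitlist v 16/24 treatment) distorts the early-impact analysis. With an assumed 15-point effect of the voucher on response, those rates imply a gap of 15 × (1 − 16/24) = 5 points. The documents do not support that size. The early-impact analysis follows the primary strategy, whose model spans all nine groups. Over both cohorts the offer is 16/32 = 50% v 16/40 = 40%, so the same assumption gives 15 × 0.10 = 1.5 points. The direction of harm is not shown either: treatment parents answer in session, so extra encouragement in the emailed arm might narrow a response gap rather than widen it.

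**Conclusion.** The point holds as a defect in what Experiment 2 can deliver. As written, the waitlist comparison is 16 v 0 families and cannot be made, and the random selection of waitlist groups is empty. This rests on the group counts, which the Protocol gives consistently in three places, and does not depend on exact group size: two out of two leaves none.

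The treatment comparison survives, so it would be wrong to say that the whole experiment fails. It does rest on a single unincentivised group. If chance leaves out the 3–5 group, the contrast is also mixed with child age and with a 12-session rather than 8-session programme.

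Severity is moderate to minor. This is a response-rate sub-study, and the primary follow-up TOPSE analysis is unaffected.

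**What to change.** In the waitlist arm, replace selection of whole groups with 1:1 randomisation of the offer among families within each group: 4 offered and 4 not in the 3–5 group, and 4 and 4 in the 6–11 group. Choosing one whole waitlist group instead would also give 8 v 8, but would confound the voucher with the child's age. Change the stated 32 families to 24 (16 treatment + 8 waitlist), and say that the waitlist result will be reported as counts with an interval and treated as descriptive only.

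Leave selection in the treatment arm at group level. Those families meet and complete the endline together in the last session, so mixed offers within a group could easily become known.

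If the team prefers to keep the offer to all waitlist families, delete the waitlist comparison from the reporting paragraph and say that Experiment 2 informs the treatment arm only.

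The first option costs a wording change and a short family-level random list, and needs 8 fewer offers (32 − 24), or up to 8 × £10 = £80 less in vouchers. The downside is small: fewer waitlist families receive the incentive, and some may learn that offers differ. The second option costs one deleted clause and the loss of the waitlist result.
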